#### **5.4. Concomitant Medication(s)**

Any medication that the subject takes other than the study drug specified in the protocol is considered concomitant medication. Information about concomitant medications will be recorded in the Case Report Form (CRF) from the screening visit through the EOT.

At the 2-week and 6-week FU Visits, only antifungal therapy the subject receives and the indication for use (eg, prophylaxis, treatment) will be recorded in the CRF. The use of non-absorbable antifungal drugs (eg, clotrimazole troches) is not required to be reported.

The recording of concomitant medications other than antifungal agents at these time points is not required unless the subject experiences an adverse event during the follow-up period, in which case all concomitant medications that the subject was receiving at the time of the adverse event must be recorded.

Treatment with another systemic antifungal agent [aside from oral nonabsorbable azoles (eg, clotrimazole troches) in not permitted, with the following exception: for the PK sub-study only (first 6 subjects aged 1 month to <2 years) administration of a second medication classified as an azole, polyene, or echinocandin will be allowed during the study treatment phase, at the Investigator's discretion.

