#### ***Important Notes:***

- Initiating or resuming oral antifungal therapy following EOT for prophylactic purposes is permitted, and does not reflect a requirement for additional systemic antifungal therapy for treatment purposes, and therefore does not constitute treatment failure. (Note: It must be clear in the project database that administration of additional antifungal therapy is for prophylactic purposes, otherwise it will be deemed as being administered for treatment of continued infection, in which case study drug treatment will be considered clinical failure). Thus, use of oral prophylactic antifungal therapy following EOT does not constitute treatment failure.
- Administration of non-absorbable antifungal agent is not considered systemic antifungal treatment in the context of this study.

**Failure:** No significant improvement in signs and symptoms, or death due to the *Candida* infection. Subjects must have received at least 3 doses of study medication to be classified as a failure.

**Indeterminate:** Evaluation cannot be made to withdrawal from the study prior to assessment of cure or failure. Subjects who receive fewer than 3 doses of study medication will be assigned as a clinical efficacy response of indeterminate.

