**8.2.4.5. Adverse Events**

All adverse events will be coded using the MedDRA dictionary. Frequencies of adverse events will be presented by system organ class, preferred term, age category, and severity level.

All causality treatment emergent adverse events will be presented using two different treatment groupings.

Firstly they will be presented for the one group where all adverse events are counted from start of study to end of follow-up period. This will provide an overall assessment of all adverse events in the study.

Secondly they will be split into time periods within the study:

- Those that occurred from start of study to end of treatment by anidulafungin, including up to end of follow-up period if no other antifungal was administered;
- Those adverse events that started after treatment with another antifungal up until the end of the follow-up period.

This will provide guidance as to which adverse events occurred during treatment with anidulafungin, as opposed to those that occurred during other therapies.

Treatment related treatment emergent adverse events will be presented in two ways:

- Firstly, for those that are considered to be caused by anidulafungin, providing a summary of treatment related adverse events;
- Secondly, for those that are caused by anidulafungin and/or fluconazole, providing a summary of adverse events for the anidulafungin plus fluconazole treatment regimen.

All causality treatment emergent adverse events and treatment related adverse events will also be summarized for the 6 subjects in the PK sub-study analysis set.

Adverse events and serious adverse events will be listed by subject for all age categories.

Adverse events leading to discontinuation or temporary dose reduction will be presented ([Discontinuation\(s\)](#) Section).

Adverse events will be reported in accordance with the sponsor reporting standards.

Additional tables summarizing adverse events that are considered to be potentially indicative of an infusion related reaction which occur during the anidulafungin infusion or within 60 minutes following completion of the anidulafungin infusion will be presented. The adverse event terms of interest are:

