#### **8.2.4.11. Use of Other Anti-Fungal Therapy**

Use of other anti-fungal therapy between EOT and Week 6 FU visit will be tabulated. Use of antifungal therapy within 30 days prior to Screening visit will also be tabulated.

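### The two-period adverse-event split in SAP 8.2.4.5 leaves some drug-free days in neither period and puts days of concomitant antifungal use in both

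*SAP*

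**What the plan says.** SAP 8.2.4.5 gives two presentations of all-causality treatment-emergent adverse events. The first is complete: "Firstly they will be presented for the one group where all adverse events are counted from start of study to end of follow-up period". The second is a split. Period 1 holds events that "occurred from start of study to end of treatment by anidulafungin, including up to end of follow-up period if no other antifungal was administered". Period 2 holds "Those adverse events that started after treatment with another antifungal up until the end of the follow-up period". The SAP states the aim of the split: "This will provide guidance as to which adverse events occurred during treatment with anidulafungin, as opposed to those that occurred during other therapies".

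Other passages foresee antifungals outside the study regimen:

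- **After treatment.** The notes to the response definitions in SAP 6.1.1.2 and 6.1.3 say: "Initiating or resuming oral antifungal therapy following EOT for prophylactic purposes is permitted". SAP 8.2.4.11 adds: "Use of other anti-fungal therapy between EOT and Week 6 FU visit will be tabulated".
- **During treatment.** In the PK sub-study, Protocol 5.4 says that "administration of a second medication classified as an azole, polyene, or echinocandin will be allowed during the study treatment phase". For subjects generally, the per-protocol criteria in SAP 5.3.1 and the imputation rules in SAP 6.1.4 both deal with antifungals taken during study therapy.

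SAP 6.2.1 has the only rule on who owns drug-free events. For an analysis it labels only as the standard required one, events up to 30 days after the last dose of study drug count as treatment emergent and are credited to the treatment taken before them. SAP 8.2.4.5 does not refer to that rule.

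**The concern.** A split by period should place each event in exactly one period. This one does not. Period 1 closes at the end of anidulafungin for any child who later receives another antifungal, and period 2 does not open until that drug is given. Whatever happens between the two is in neither.

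The classification of an early event also depends on what is done later. An event 5 days after the last anidulafungin dose is in period 1 for a child who gets nothing further. The same event is in neither period for a child who starts prophylaxis on day 14 after the last dose. Where the two drugs are taken together, the reverse happens and an event can be counted in both periods.

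Safety is the primary endpoint, and this split is the plan's tool for separating events under anidulafungin from events under other therapies. If a reader compares the two columns, events missing from both, or present in both, weaken that comparison.

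**Working it through.** The plan states no figure on this point, so there is none to reproduce. The check assigns study days to the two periods.

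**Inputs**

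- L = day of the last anidulafungin dose; S = first day of the other antifungal; F = last day of follow-up.
- Period 1 (SAP 8.2.4.5): Day 1 to L if another antifungal is given, Day 1 to F if none is.
- Period 2 (SAP 8.2.4.5): S to F, reading it as opening on the day the other drug starts.
- Follow-up: 6 weeks after EOT (Protocol 3), nominally 42 days; the visit window in SAP Appendix 1.1 is 35 to 49 days. For a child on IV anidulafungin only, EOT is L.
- Assumptions, not from the documents: 14 days of IV treatment, so L = 14 and F = 14 + 42 = 56; other antifungal starting g days after L, so S = L + g.

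**Gap.** Days L + 1 to S − 1 are in neither period, so unassigned days = g − 1.

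| Other antifungal | Period 1 | Period 2 | Neither | Share of 42 days |
|---|---|---|---|---|
| none | 56 | 0 | 0 | 0% |
| g = 1 (next-day switch) | 14 | 42 | 0 | 0% |
| g = 7 | 14 | 36 | 6 | 6/42 = 14% |
| g = 14 | 14 | 29 | 13 | 13/42 = 31% |
| g = 28 | 14 | 15 | 27 | 27/42 = 64% |

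Each row sums to 56. The SAP does not say where the start day itself belongs. If it is left out of period 2, each gap grows by one day.

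**Which reading of period 2.** The text could also mean after the other antifungal has ended. Take a child with 10 days of IV treatment and oral fluconazole on Days 11 to 24. That reading would leave 24 − 10 = 14 on-fluconazole days in neither period, against the stated aim of showing events during other therapies. The start reading is therefore used here.

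**Overlap.** If S falls on or before L, days S to L are in both periods, which is L − S + 1 days. For a PK sub-study child on combination therapy from Day 1 who stops anidulafungin after the Day 2 sampling, this is 2 − 1 + 1 = 2 days, and longer if sampling is postponed. For any child given another antifungal on Day 3 of a 14-day course, it is 14 − 3 + 1 = 12 days.

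**Effect of the 30-day rule, if it applied.** Days L + 1 to L + 30 would go to anidulafungin. The 6, 13 and 27 unassigned days would all become 0. A start at g = 42 leaves 41 unassigned days, of which 41 − 30 = 11 would remain.

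**The case against.** The strongest reply is that SAP 6.2.1 already says who owns drug-free events: they go to the preceding treatment for up to 30 days. Applied to the split, that would close every gap in the table above. It deserves weight, and it may be what the authors had in mind. But the rule is confined to an analysis that the SAP does not tie to any table, and 8.2.4.5 does not invoke it. A programmer working from 8.2.4.5 alone would not apply it. It also does nothing for the overlap.

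The second reply is that little depends on this. That largely stands. The split is the second of two presentations and is offered as guidance, the study is descriptive with no hypothesis tests, and a direct switch to fluconazole creates no gap.

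A reader might infer more than the documents support in two ways:

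- **That events drop out of the primary safety analysis.** They do not. The overall presentation runs from start of study to end of follow-up, in line with Protocol 9.1, and events are also listed by subject.
- **That the main tables are cut at 30 days.** The opening rule in 6.2.1 has no upper limit. The next sentence says that events within 30 days count, without saying that later ones are excluded. Both sections defer to sponsor reporting standards, which are not available here and may define that analysis. What is left is a missing cross-reference.

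Nor is the overlap confined to the six PK sub-study children, because SAP 5.3.1 and 6.1.4 foresee concomitant antifungals in any subject.

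**Conclusion.** The point holds as a minor correction to the second presentation in SAP 8.2.4.5. As written, the two periods are neither exhaustive nor mutually exclusive, and later treatment can decide whether an earlier event is shown in the split at all.

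The illustrated size is 6 to 27 of 42 follow-up days for a child who starts another antifungal 7 to 28 days after the last anidulafungin dose. It is zero for a child given no other antifungal or switched the next day. These are days, not events: the start days are assumed, and the documents give neither event rates nor the number of children who would start a later antifungal. The figures also assume that period 2 includes the start day and that the 30-day attribution rule does not apply to this table.

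**What to change.** In SAP 8.2.4.5, divide the periods at a single date:

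- **Period 1:** from the first anidulafungin dose to the day before the first day, after the last anidulafungin dose, on which another systemic antifungal is taken; if there is no such day, to the end of follow-up. State that oral fluconazole counts as another antifungal here.
- **Period 2:** from that day to the end of follow-up.

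Events during concomitant use up to the last anidulafungin dose then fall in period 1, a brief concomitant course does not move later follow-up into period 2, and each event is counted once. As a clarification in SAP 6.2.1, say which tables, if any, use the 30-day limit, and that the 8.2.4.5 tables run to the 6-week visit.

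The cost is SAP wording. No new data are needed. Protocol 8.2 has adverse events recorded through the last visit, and for the follow-up visits Protocol 5.4 says "only antifungal therapy the subject receives and the indication for use (eg, prophylaxis, treatment) will be recorded in the CRF". The 2-week visit is required only in confirmed infection, but at the 6-week visit Protocol 6.6 asks for systemic antifungal use since the last study visit. This assumes that the CRF holds antifungal dates, which the day-count rules in SAP 6.1.4 also need.

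The downside is that period 1 includes some drug-free time, as it already does for children given no other antifungal. A separate off-drug category would also close the gap, if the sponsor prefers to show that time on its own.

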#### **8.2.4.6. Laboratory Data**

Descriptive statistics will be summarized by age category for each baseline measurement as well as for median changes from baseline at each post dose measurement time for laboratory parameters. A listing of laboratory data values and changes from baseline will be provided by age category, subject, test and time.

For each age category, a summary table will present the frequency of subjects with post dose laboratory test abnormalities. All post dose visits will be counted. Listings of values of potential clinical concern will be provided by both subject and by test.

All presentations of laboratory test data will be in accordance with the sponsor reporting standards.

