10. The 'screening visit culture' is the culture result that qualifies the subject with definitive diagnosis of ICC for study entry (along with other inclusion criteria) and is from a blood or tissue sample that was obtained within 96 hours prior to the screening visit, that is positive for *Candida* sp. The result of this culture will be recorded on the 'screening visit' case report form. In the event the culture result from this sample is pending, plan to record the culture result on the screening visit case report form once the organism has been identified and the information is available. Please note: if the day of the screening visit is also Day 1 of treatment, a sample of blood for culture will be obtained; otherwise a sample of blood for culture is not required until the first day of treatment (Day 1), just prior to administration of study drug.
11. A blood culture at the 2-week and 6-week follow-up visit is required only if clinically indicated.
12. Cultures of other sterile sites will be collected as clinically indicated. Pathogen isolated will be documented.
13. CBC with differential (including RBC count, reticulocytes, white blood cells, neutrophils, lymphocytes, monocytes, basophils, and platelet count), and serum chemistry tests (AST, ALT, Alk-Phos, total Bilirubin, Albumin, BUN or Urea, Cr, Bicarbonate, Glucose, Na, K, Ca, Cl, Mg) are to be repeated on Day 3, 7 and every seven days during treatment phase, and repeated at both follow-up visits.
14. Hematology and chemistry tests should be repeated at both follow-up visits.
15. An echocardiogram at the time of screening is not required if the test was already performed within the previous 96 hours (of the screening visit). The results of the echocardiogram, however, must be recorded in the case report form. (Not applicable to Korean and Portuguese investigator sites.)

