## 2. STUDY OBJECTIVES AND ENDPOINTS

### 2.1. Objectives

#### Primary

- To assess the safety and tolerability of anidulafungin when used to treat children with invasive candidiasis, including candidemia.

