Subjects without microbiologically confirmed *Candida* infection will be treated with IV anidulafungin at the discretion of the investigator to a maximum of 35 days. Subjects may be switched to oral fluconazole (6-12 mg/kg/day, maximum 800 mg/day) after at least 5 days of IV anidulafungin treatment.

The maximum total treatment duration for all subjects in this study is 49 days, and the maximum allowed treatment duration with anidulafungin is 35 days. The last day of study treatment will be considered the EOT. Subjects will be followed in the study for a total of 6 weeks after EOT. It is expected that the majority of subjects will receive study drug in the hospital; subjects will be permitted to complete study medication on an outpatient basis if deemed appropriate by the investigator.

*(The following two paragraphs are not applicable to Korean and Portuguese investigator sites.)*

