### **9.1. Analysis of Primary Endpoint**

The primary analysis will be the evaluation of adverse events throughout the trial, laboratory tests, and physical examination.

The set of subjects for this evaluation will be the Safety population, defined as all subjects with at least 1 dose of study medication.

The following parameters will be summarized: rates of discontinuation, adverse events, ECG findings (if applicable), and laboratory abnormalities.

The Sponsor has standard algorithms for reporting adverse events and clinical laboratory test results, and these will be employed in the analysis of the data from this trial. Safety data will be subject to clinical review and summarized by appropriate descriptive statistics. Descriptive statistics for categorical data will include frequencies and/or percentages.

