### 8.2.1. Primary Analysis

The primary analysis is to examine safety and tolerability of anidulafungin. The set of subjects for this evaluation will be the Safety population. The following parameters will be summarized: rates of discontinuation, adverse events, visual tests, physical examination, ECG findings (if applicable), and laboratory abnormalities. The analysis methods are described in [Section 8.2.4](#).

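### Laboratory abnormalities are tabulated only over all post-dose visits, so the planned frequency is a whole-study rate and does not describe anidulafungin alone

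*SAP*

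**What the plan says.** The primary objective in Protocol 2.1 is "To assess the safety and tolerability of anidulafungin when used to treat children with invasive candidiasis, including candidemia". Protocol 9.1 makes laboratory data part of the primary analysis: "The primary analysis will be the evaluation of adverse events throughout the trial, laboratory tests, and physical examination". SAP 8.2.1 agrees; its list of parameters ends with "visual tests, physical examination, ECG findings (if applicable), and laboratory abnormalities", and it refers to SAP 8.2.4 for methods.

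The counting rule is in SAP 8.2.4.6. For each age category a table gives the "frequency of subjects with post dose laboratory test abnormalities. All post dose visits will be counted". The same section also plans median changes from baseline at each measurement time, listings by subject, test and time, and listings of values of potential clinical concern. Appendix 2, the SAP's only list of output tables (written for the interim analysis), names three laboratory incidence tables: regardless of baseline, normal baseline and abnormal baseline. None is by treatment period.

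Adverse events are handled differently. SAP 8.2.4.5 keeps an overall table and adds a split into two periods. The first runs to the end of anidulafungin and extends through follow-up where no other antifungal was given. The second holds events that began after another antifungal. The stated reason is: "This will provide guidance as to which adverse events occurred during treatment with anidulafungin, as opposed to those that occurred during other therapies".

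**The concern.** A subject enters the laboratory table if any post-dose panel is abnormal. That includes panels taken on oral fluconazole and those taken weeks after all study treatment has ended. The table therefore answers how often an abnormality occurred at any time in the study. The primary objective concerns anidulafungin, and Protocol 7.7 singles out liver tests for careful monitoring.

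The separation matters at least as much here as for adverse events. An adverse event carries an investigator's causality assessment. A row in an abnormality table does not, so timing is the main information a reader has on attribution.

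The table is also by age category. Infants at high risk without confirmed infection can enroll only under 2 years (Protocol 4.1). Subjects without confirmed infection may switch to oral therapy earlier (Protocol 5.1) and need no 2-week visit (Protocol 6.5). The number of panels, and the share drawn on anidulafungin, can thus differ between strata with no difference in drug effect.

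**Working it through.** The documents state no laboratory abnormality rate, so there is no figure to reproduce. The check counts scheduled panels by period and then illustrates what the count implies.

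**Inputs**
- Panels on Day 3, Day 7 and every seven days during treatment (Schedule of Activities, footnote 13), at end of IV therapy (Protocol 6.3) and at end of oral therapy (Protocol 6.4).
- Follow-up at 2 and 6 weeks: "Hematology and chemistry tests should be repeated at both follow-up visits" (Schedule of Activities, footnote 14).
- Durations: "The maximum total treatment duration for all subjects in this study is 49 days, and the maximum allowed treatment duration with anidulafungin is 35 days" (Protocol 5.1). With confirmed infection, an oral switch is optional after at least 10 days IV.
- Week 6 analysis window: EOT + 35 to EOT + 49 days (SAP Appendix 1.1).

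**Panel counts, confirmed infection** (weekly oral-phase panels counted from the end-of-IV panel)

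| Course | IV | Oral | Follow-up | After last anidulafungin dose |
|---|---|---|---|---|
| 35 days IV only | 6 (Days 3, 7, 14, 21, 28, 35) | 0 | 2 | 2 of 8 (25%) |
| 14 days IV only | 3 (Days 3, 7, 14) | 0 | 2 | 2 of 5 (40%) |
| 10 days IV, oral to Day 24, no weekly oral panels | 3 (Days 3, 7, 10) | 1 (Day 24) | 2 | 3 of 6 (50%) |
| Same, weekly oral panels | 3 | 2 (Days 17, 24) | 2 | 4 of 7 (57%) |
| 10 days IV, oral to Day 49, weekly oral panels | 3 | 6 (Days 17, 24, 31, 38, 45, 49) | 2 | 8 of 11 (73%) |

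Two rows depend on weekly panels continuing on oral therapy. Footnote 13 says treatment phase, which supports that. The schedule's weekly column covers Days 11 to 34, and Protocol 6.2.7 ties it to IV therapy. Without weekly oral panels, the Day 49 course also has 3 of 6.

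**Illustration.** If each panel has an independent chance p of an abnormality, unrelated to drug, the chance of at least one in k panels is 1 − (1 − p)^k. Each cell gives the IV-period rate, then the all-visit rate, then their ratio.

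| Course | p = 2% | p = 5% | p = 10% |
|---|---|---|---|
| 35 days IV only (k = 6, 8) | 11.4%, 14.9%, 1.31 | 26.5%, 33.7%, 1.27 | 46.9%, 57.0%, 1.22 |
| 14 days IV only (3, 5) | 5.9%, 9.6%, 1.63 | 14.3%, 22.6%, 1.59 | 27.1%, 41.0%, 1.51 |
| Oral to Day 24, no weekly (3, 6) | 5.9%, 11.4%, 1.94 | 14.3%, 26.5%, 1.86 | 27.1%, 46.9%, 1.73 |
| Oral to Day 24, weekly (3, 7) | 5.9%, 13.2%, 2.24 | 14.3%, 30.2%, 2.12 | 27.1%, 52.2%, 1.93 |
| Oral to Day 49, weekly (3, 11) | 5.9%, 19.9%, 3.39 | 14.3%, 43.1%, 3.02 | 27.1%, 68.6%, 2.53 |

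**Comparison with the adverse-event rule.** In the two IV-only rows, if no other antifungal is given, SAP 8.2.4.5 would keep every panel in the anidulafungin period. In the three oral rows it would move 3, 4 or 8 panels to the second period. There the all-visit rate is 1.7 to 3.4 times the IV-period rate under the same assumptions.

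**The case against.** The best defense is that counting all visits is the inclusive choice for safety and catches delayed effects. It also agrees with SAP 8.2.4.5 for subjects who receive nothing after anidulafungin. That stands: a reader might infer that counting Week 2 and Week 6 panels always contradicts the adverse-event approach, and it does not.

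A reader might also infer that the rate fails to describe anidulafungin at all, or attributes fluconazole effects to it. The documents do not support that. "All post dose visits will be counted" takes in every anidulafungin panel, the study is descriptive (SAP 4), and a frequency table makes no causal claim. Nor would a split remove confounding by acute illness and other drugs during the IV period.

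A third tempting step is to make a table cut at the last IV dose plus 2 days the primary laboratory summary. The 2 days in SAP Appendix 1.1 allocate observations to visits and do not define a risk period. The SAP's post-treatment adverse-event lag is 30 days (SAP 6.2.1). With a terminal half-life of 40 to 50 hours (Protocol 1.3.2), 48 hours is about one half-life, so such a cut could move delayed abnormalities out of the main table.

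Part of the information does appear elsewhere. Abnormalities that are symptomatic or need action become adverse events (Protocol 8.4), and potential Hy's Law cases become serious ones (Protocol 8.5.2). Both then enter the period split. But medians hide individual outliers, listings give no incidence, and adverse events capture only a subset. None gives the frequency of abnormal tests in the anidulafungin period. The sponsor reporting standards might set a window. Their content is not in the documents, and the explicit sentence in SAP 8.2.4.6 points the other way.

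**Conclusion.** The point holds as a missing table. As specified, the laboratory abnormality frequency covers the whole study, and no planned output gives a frequency for the anidulafungin period. The SAP recognizes the same need for adverse events and meets it there.

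The effect is clearest in subjects who receive fluconazole or another antifungal. The switch is optional, so the number affected is unknown in advance. Between a quarter and nearly three quarters of scheduled post-dose panels fall after the last anidulafungin dose in the courses examined; the top of that range needs minimum IV therapy, maximum total duration and weekly oral-phase panels together.

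The ratios of about 1.2 to 3.4 rest on an assumed constant per-panel probability of 2% to 10% and on independence between panels. Results from the same sick child are likely to be positively correlated, which would shrink the gap. The documents do not allow the true size to be derived.

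**What to change.** Keep the all-visits table as the primary laboratory summary. Add to SAP 8.2.4.6 and to the table list (Appendix 2 and its final-analysis counterpart) a frequency table by age category with the split already used in SAP 8.2.4.5:

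- (i) first dose to end of anidulafungin, including follow-up where no other antifungal was given, with on-treatment and follow-up panels in separate columns;
- (ii) panels after the start of fluconazole or another antifungal.

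Do not adopt a 2-day cut as the risk window. State which period takes an end-of-IV panel drawn once fluconazole has started, and how panels are placed for PK sub-study infants given a second antifungal alongside anidulafungin.

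The dosing and sampling dates needed are already collected, so no new data are required. The cost is a few table columns and small counts per cell, with about 20 evaluable subjects planned per age stratum.
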